12.1.3 Imaging Aims and Statistics

There are three imaging aims in this correlative study, which will be based on central review of the acquired ¹⁸F-FDG PET/CT scans, and which are distinguished into primary and secondary.

Imaging aims which involve patient outcomes (overall survival or progression-free survival) will be conducted at full information. In

addition, reporting of imaging aims will not be done prior to reporting of the respective primary or secondary therapy endpoints.

12.1.3.1 Primary imaging aim

[1] To evaluate the association between baseline ¹⁸F-FDG PET/CT and patient outcomes.

The primary imaging aim consists of evaluating the association between baseline ¹⁸F-FDG PET/CT and patient outcomes, and seeks to address the question of whether abnormal ¹⁸F-FDG PET/CT findings at baseline (i.e., after approximately 1 year of lenalidomide maintenance following an early stem cell transplant) are prognostic of poorer progression-free survival (PFS) and overall survival (OS). The potential association will be analyzed using both quantitative and qualitative ¹⁸F-FDG PET/CT parameters.

Rev. Add3

Quantitatively, the association between baseline SUV-based quantitative ¹⁸F-FDG PET/CT parameters (SUVmax, SUVpeak, MTV, TLG) and PFS will be analyzed through Cox regression. PFS will be defined as the time from randomization until the earlier of progression or death due to any cause. SUV-based quantitative ¹⁸F-FDG PET/CT (qPET) parameters will be analyzed as continuous covariates, and adjustment will be made for potential confounders, including patient age and the randomization stratification factors. In addition, we will formally test whether this association differs by study arm through a statistical interaction term between the qPET parameter and study arm. If this interaction is not significant at the 0.05 level, then a single overall hazard ratio will be estimated for the entire study cohort. We assume that up to 10% of patients may not receive the ¹⁸F-FDG PET/CT at baseline or may have an uninterpretable scan.

Standardizing each qPET parameter to have mean 0 and standard deviation 1, and assuming the R-square of each qPET parameter with other covariates is no more than 0.4, the proposed sample size of 510 patients (459 evaluable) has power of 82% to detect a hazard ratio as low as 1.25 per standard deviation increase in the qPET parameter, when the progression event rate is 0.6. If the observed progression event rate over the duration of the trial is higher than 0.6, the power will correspondingly increase (e.g., power=85% for a progression event rate of 0.65). A two-sided Cox regression with a type I error rate of 0.05 was used for this computation (PASS 16). In addition, for further clinical utility, we will explore estimating an optimal threshold for each baseline qPET parameter using recursive partitioning in a conditional inference framework, with 95% confidence interval derived using the bootstrap technique.⁵⁰ Finally, since a marker displaying an independent, strong association may not necessarily contribute meaningfully to improved classification, we will

also examine the ability of each baseline qPET parameter to serve as a prognostic marker in discriminating patients which progress within 2 years and 3 years of the start of study mandated therapy using time-dependent (cumulative sensitivity/dynamic specificity) ROC analysis.^{51,52} Area under the time-dependent ROC curve [AUC(t)] will be estimated using the NNE method proposed by Heagerty.^{53,54}

Qualitative criteria are described in protocol Section [12.1.2](#). These criteria will be used to dichotomize the baseline ¹⁸F-FDG PET/CT scans as either negative or positive, where analyses using the IMPETUS and IMAJEM criteria are considered exploratory. The association between a positive/abnormal baseline ¹⁸F-FDG PET/CT scan and PFS will be assessed through Kaplan-Meier curves with the log-rank test. An adjusted analysis will also be conducted using a Cox regression model, with adjustment for potential confounders, including patient age and the randomization stratification factors. In addition, we will formally test whether this association differs by study arm through a statistical interaction term between ¹⁸F-FDG PET/CT positivity and study arm. If this interaction is not significant at the 0.5 level, then a single overall hazard ratio will be estimated for the entire study cohort. It is anticipated that between 50-70% of patients will have a positive ¹⁸F-FDG PET/CT scan at baseline. Assuming 60% of patients have a positive ¹⁸F-FDG PET/CT scan at baseline, the proposed sample size of 510 patients (459 evaluable) yields 87% power at a type I error rate of 0.05 to detect a difference in median PFS between ¹⁸F-FDG PET/CT-positive and ¹⁸F-FDG PET/CT-negative patients as low as 7 months (19 vs. 26 months, respectively, assuming 3 years of accrual time and 4.5 years of patient follow-up; PASS 16).

Similar analyses will be conducted for the OS outcome. OS will be defined as the time from randomization until death or the date last known alive.

The ¹⁸F-FDG PET/CT images will be collected centrally and archived for future research analysis. All data and results will be anonymized.

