5.8 Duration of Follow-up

For this protocol, all patients, including those who discontinue protocol therapy early, will be followed for response until progression, even if non-protocol therapy is initiated, and for survival for 10 years from the date of randomization. All patients must also be followed through completion of all protocol therapy.

6. Measurement of Effect

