9.3.2 Secondary Clinical Analyses

Progression-Free Survival (PFS)

An important secondary aim is to evaluate whether a response-adapted strategy translates into superior progression-free survival for patients switching to more-intensive treatment. PFS will be estimated using the KM method and compared using the stratified log-rank test. Median PFS on the control arm is assumed to be 18 months based on results from recent clinical trials. Assuming exponential distribution of failures, this study is design to detect a 44% increase in median PFS to 26 months on the experimental arm. This corresponds to a treatment HR approximating 0.70 [monthly hazard rate 0.0385 versus 0.0267]. At 1-sided 2.5% type I error, there is approximately 90% power using a log-rank test to detect this HR given 510 patients uniformly accrued over 3.5y with full information of 319 PFS events at 4.5y (accrual end plus one year). The actual timing of this PFS analysis will depend on accrual. The analysis will not be done before one year after the last patient is randomized. No interim analyses for the PFS comparison will be conducted. The study team will also not consider or declare the experimental arm to be a success based on the PFS endpoint alone.

Response

Response will be tabulated by category. Response rates (sCR, CR, VGPR) will be compared using the chi-squared test for proportions. It is hypothesized that the ixazomib-lenalidomide arm will have higher response rates. Ineligible patients are excluded from the analysis and unevaluable patients are counted in the denominator. Sensitivity analyses will exclude unevaluable patients from the rate calculations. Given 255 patients per arm, there is over 90% to detect a difference of 15% in VGPR rates at 1-sided 2.5% significance assuming a 52.5% overall VGPR rate.

Toxicity

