9.4 Sample Size Considerations

Rev. Add1

OS will be estimated based on the KM method and compared between arms using the stratified log-rank test. All survival estimates are from randomization, which would be ~18 months from start of initial therapy. Median OS for the control arm was estimated to be 5.5 years (y) considering expectations in this setting for an unselected cohort as well as results from the previously mentioned meta-analysis according to post-treatment MRD status.³ Based on the log-rank test, there is approximately 80% power at 1-sided 2.5% significance to detect a difference in 4y OS from 60.4% to 72.2% reflecting an approximate 35% reduction in hazard [treatment HR=0.65] assuming 510 patients uniformly accrued over 3.5y and 179 deaths at full information (6y).

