9.5 Projected Accrual

This study aims to screen 840 patients to pre-registration Step 0 at an accrual rate of 20 patients per month/240 patients per year for an accrual duration of 3.5y. With an allowance of 15% for patients not yielding high quality specimens for MRD analysis, it is expected that 714 patients will have MRD measured. MRD status is anticipated to be split 75% positive/25% negative resulting in 536 MRD positive patients and 178 MRD negative patients. Some drop-out (5%) between marker evaluation and enrollment to Step 1 treatment is also anticipated resulting in an estimated 510 patients randomized to Arm A or Arm B with 1:1 allocation. Patients with MRD negative disease status based on NGF and immunofixation results will not be registered to the treatment phase.

Rev. Add3

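### The 87% power for the PET-positive versus PET-negative PFS comparison needs an analysis at 7.5 years that is not planned; it is about 73% at PFS full information and about 83% at 6 years. The interaction cut is also printed as 0.5.

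*Combined protocol and SAP*

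**What the plan says.** For the dichotomised baseline scan, section 12.1.3.1 claims 87% power at a type I error rate of 0.05 with 459 evaluable of 510 patients, 60% of them PET-positive, and median PFS of 19 versus 26 months, "assuming 3 years of accrual time and 4.5 years of patient follow-up; PASS 16". It expects 50–70% of patients to be PET-positive.

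The timing of that analysis is set elsewhere:

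- Section 12.1.3: "Imaging aims which involve patient outcomes (overall survival or progression-free survival) will be conducted at full information".
- Section 9.3.2, for PFS: 90% power "given 510 patients uniformly accrued over 3.5y with full information of 319 PFS events at 4.5y (accrual end plus one year"), and "The analysis will not be done before one year after the last patient is randomized".
- Section 9.4, for OS: "assuming 510 patients uniformly accrued over 3.5y and 179 deaths at full information (6y").
- Section 9.5 also plans recruitment "for an accrual duration of 3.5y".
- Section 5.8: patients "will be followed for response until progression, even if non-protocol therapy is initiated, and for survival for 10 years from the date of randomization".

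On the PET-positivity-by-arm interaction, section 12.1.3.1 says "If this interaction is not significant at the 0.5 level", a single hazard ratio is estimated for the whole cohort. The same rule for the quantitative PET parameters, earlier in that section, uses 0.05. So does the treatment-by-PET interaction test in section 12.1.3.2.

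**The concern.** In section 9.3.2 the 4.5 years is total study time: 3.5 years of accrual plus one. In section 12.1.3.1 the same number appears as follow-up on top of 3 years of accrual. If it was used that way, the power belongs to a much more mature data set than the one the plan will analyse. A reader would credit this part of the primary imaging aim with a type II error of 13% when it is about 27% at PFS full information, and could read too much into a null result.

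The 0.5 cut is a separate matter. It decides whether one overall hazard ratio is reported. With no true interaction the p-value is uniform, so a 0.5 cut would withhold the pooled estimate about half the time, against 5% of the time at 0.05.

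**Working it through.** **Inputs.** From section 12.1.3.1: n = 459, 60% PET-positive (275.4 versus 183.6), medians 19 and 26 months, alpha 0.05. The power sentence does not state sidedness. The companion quantitative PET calculation in the same section is two-sided, so two-sided is assumed. Exponential PFS and uniform accrual are also assumed, as in section 9.3.2.

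**Formulas.** Hazards are λ = ln 2 / median: 0.03648 and 0.02666 per month, so the log hazard ratio is ln(26/19) = 0.3137. With accrual A and analysis time T in months, the expected events in a group of size m are

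d = m × {1 − [exp(−λ(T−A)) − exp(−λT)] / (λA)}.

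Power by Schoenfeld, with D total events, is Φ(0.3137 × √(D × 0.6 × 0.4) − 1.96). A second version replaces the standard error by √(1/d₁ + 1/d₂). Log-rank simulation (10,000 runs per scenario) is a third check.

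**The plan's own figure.** Take A = 36 and T = 36 + 54 = 90 months. Events are 254.0 + 155.6 = 409.6. Then 0.3137 × √(409.6 × 0.24) = 3.110, and Φ(3.110 − 1.960) = Φ(1.150) = 87.5%. The stated 87% is reproduced, with 410/459 = 89% of patients having an event.

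**PFS full information.** Section 9.3.2's own inputs (510 patients, medians 18 and 26 months, 3.5 years of accrual, 4.5 years total) give 319.0 events, matching the plan. Scaled to the evaluable patients, 319 × 459/510 = 287. Direct calculation with A = 42 and T = 54 gives 184.4 + 103.4 = 287.8 events, and Φ(2.607 − 1.960) = Φ(0.647) = 74.1%.

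**OS full information.** A = 42 and T = 72 gives 362.2 events, and Φ(2.924 − 1.960) = Φ(0.964) = 83.3%.

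| Accrual, analysis time | Events | Schoenfeld | 1/d₁ + 1/d₂ | Simulation |
|---|---|---|---|---|
| 3 y, 7.5 y | 410 | 87.5% | 86.9% | 86.6% |
| 3.5 y, 7.5 y | 404 | 87.0% | 86.4% | 86.0% |
| 3 y, 4.5 y | 306 | 76.7% | 75.1% | 74.6% |
| 3.5 y, 4.5 y | 288 | 74.1% | 72.3% | 73.3% |
| 3.5 y, 6 y | 362 | 83.3% | 82.2% | 83.2% |

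The 3 versus 3.5 years of accrual hardly matters with the analysis held at 7.5 years (87.5% to 87.0%). The analysis time drives the gap.

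**Range over PET positivity** (3.5 years of accrual, across the three methods):

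| PET-positive | 4.5 y | 6 y |
|---|---|---|
| 50% | about 75% | about 84% |
| 60% | 72–74% | 82–83% |
| 70% | 66–69% | 76–79% |

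**What 87% would take.** By Schoenfeld, 87% needs about 403 events, reached at about 7.5 years with 3.5 years of accrual; 80% needs about 332 events, at about 5.3 years. At 4.5 years, 87% requires medians of about 19 versus 27.6 months, a difference of 8.6 months instead of 7.

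**Companion calculation.** For the quantitative PET parameters (hazard ratio 1.25 per SD, R-square 0.4), power is Φ(ln 1.25 × √(459 × 0.6 × (1 − 0.4)) − 1.96) = 81.8% at an event rate of 0.6, and 84.7% at 0.65. These match the stated 82% and 85%, and the event rates agree with 319/510 = 62.5%. So one aim rests on event rates of about 0.6 and about 0.89 in the same 459 patients.

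**The case against.** The strongest reply is that the 87% is not miscalculated: it follows from the inputs printed beside it. That is true. The fault is that those inputs do not describe an analysis the plan contains.

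Sidedness is not stated in the power sentence. A one-sided 0.05 test with 3 years of accrual and 4.5 years in total gives 84–85%, which comes near. But the companion calculation is two-sided, the match is poorer, and with the trial's 3.5 years of accrual the one-sided figure is 82–83%. This reading does not rescue the 87%, though it does show that sidedness needs stating.

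Section 12.1.3 does not say which full information it means. If it is OS at 6 years, the shortfall is only about 4 points. This objection partly stands, and both figures are therefore given. The PFS reading is better supported: section 12.1.3 ties imaging reports to the respective therapy endpoint, and the companion calculation uses an event rate of 0.6.

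Follow-up continues well past 4.5 years, and section 9.3.2 lets the PFS date move with accrual. Later data will exist, but a trigger of 319 events fixes the information whatever the date.

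Finally, this is one correlative comparison that does not size the trial, and a null result would be read from its estimate and interval as well as its p-value. The 0.5 is very likely a slip, and the text does not say what is reported if the interaction is significant. These points limit the importance; they do not make the printed figures right.

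**Conclusion.** The concern holds. The 87% corresponds to about 410 events at 7.5 years. The plan's PFS full information gives about 288 events in the evaluable patients and about 73% power (72–74% by method); OS full information at 6 years gives about 83%. If 70% are PET-positive, these fall to 66–69% and 76–79%. The figures assume exponential PFS, uniform accrual over 3.5 years, 10% unevaluable scans and a two-sided 0.05 test. Only the dichotomised PFS comparison is affected; the quantitative PET power and the treatment comparisons are not. The 0.5 interaction cut conflicts with the two parallel rules and is wrong as printed.

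**What to change.** In section 12.1.3.1, give accrual as 3.5 years, state that the test is two-sided, and say which full information applies. Then either state about 73% power at PFS full information (about 288 events in 459 evaluable patients), or set this analysis at 6 years and state about 83%. Give the range over 50–70% PET-positive. Separately, change the PET-positivity-by-arm interaction threshold from 0.5 to 0.05.

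The cost is protocol text only. Sample size, data collection and the treatment comparison do not change. The stated power for this one comparison becomes less favourable.

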12.1.3.2 Secondary imaging aims

[2] To compare overall survival (OS) with the addition of ixazomib to lenalidomide among baseline ¹⁸F-FDG PET/CT-positive and ¹⁸F-FDG PET/CT-negative subgroups.

This secondary imaging aim consists of a subgroup analysis of the trial primary endpoint, and will assess for heterogeneity of treatment effect by baseline ¹⁸F-FDG PET/CT status. If such heterogeneity is detected, this

would suggest that the effectiveness of ixazomib treatment could be increased by targeting patients with the appropriate baseline ^{18}F -FDG PET/CT status.⁵⁵

Heterogeneity of treatment effect will be assessed at full information, using a two-sided statistical test for interaction between study arm (ixazomib/lenalidomide vs. placebo/lenalidomide) and baseline ^{18}F -FDG PET/CT status (positive/abnormal vs. negative) in a Cox regression model.^{56,57} If the statistical test for interaction is not significant at the 0.05 level, we will conclude that there is not sufficient evidence for heterogeneity of treatment effect; if the statistical test for interaction is significant, estimated treatment hazard ratios for OS (ixazomib arm vs. placebo arm) will be reported separately for baseline ^{18}F -FDG PET/CT-positive and ^{18}F -FDG PET/CT-negative subgroups, along with the corresponding 95% confidence intervals. OS will be defined as the time from randomization until death or the date last known alive.

We anticipate between 50-70% of patients will have a positive ^{18}F -FDG PET/CT scan at baseline. Sensitivity of the findings will be examined by adjusting the Cox model for patient age and the randomization stratification factors.

[3] To compare the change in quantitative ^{18}F -FDG PET/CT parameters over time with the addition of ixazomib to lenalidomide.

This secondary imaging aim consists of comparing the change in ^{18}F -FDG PET/CT parameters over time across study arms and seeks to address the question of whether adding ixazomib to lenalidomide results in sharper decreases in ^{18}F -FDG uptake (as measured by ^{18}F -FDG PET/CT) compared to lenalidomide plus placebo, thus giving evidence of greater disease control.

The difference in qPET parameters from the baseline ^{18}F -FDG PET/CT to the year 1 ^{18}F -FDG PET/CT will be reported by study arm. An analysis of covariance (ANCOVA) model will be used to test for a treatment effect on each qPET parameter, where the baseline qPET parameter value and an indicator for study arm are included as covariates, with the qPET parameter at year 1 as the model outcome.⁵⁹⁻⁶¹ Sensitivity of the findings will be examined by additionally adjusting the ANCOVA model for the randomization stratification factors (, as this would be expected to further improve precision of the study arm comparison.⁶²

In addition, longitudinal profiles of each qPET parameter from the baseline ^{18}F -FDG PET/CT through the year 2 ^{18}F -FDG PET/CT will be compared across study arm through an appropriately constructed linear mixed model.⁶³

Assuming that up to 15% of patients may not have either the baseline ^{18}F -FDG PET/CT scan performed or the year 1 ^{18}F -FDG PET/CT scan performed, or may have one or more of these scans uninterpretable, the proposed sample size of 510 patients (434 evaluable, 217 per study arm) has power of 80% using ANCOVA at a type I error rate of 0.05 to detect a difference in year 1 mean SUVmax between arms as low as 2.0, with only moderate correlation between the baseline and year 1 SUVmax ($R^2=0.45$) and common standard deviation as large as 10.0 (PASS 16). Larger correlation between baseline and year 1 SUVmax and/or smaller standard deviation of SUVmax would result in greater power.

13. Electronic Data Capture

Please refer to the EAA171 Forms Completion Guidelines for the forms submission schedule. Data collection will be performed in Medidata Rave and TRIAD.

Rev. Add1

Data for this study will be submitted via the Data Mapping Utility (DMU). Cumulative protocol- and patient-specific data will be submitted weekly to CTEP electronically via the DMU. DMU Light reporting consists of Patient Demographics, On/Off Treatment Status, Abbreviated Treatment and Course information, and Adverse Events as applicable. Instructions for setting up and submitting data via DMU are available on the CTEP Website: <https://ctep.cancer.gov/protocolDevelopment/dmu.htm>.

NOTE: All adverse events (both routine and serious) that meet the protocol mandatory reporting requirements must be reported via DMU in addition to expedited reporting of serious adverse events via CTEP-AERS.

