2.5 Imaging Objectives

- 2.5.1 To evaluate the association between baseline ¹⁸F-FDG PET/CT and patient outcomes.
- 2.5.2 To compare overall survival (OS) with the addition of ixazomib to lenalidomide among baseline ¹⁸F-FDG PET/CT-positive and ¹⁸F-FDG PET/CT -negative subgroups.
- 2.5.3 To compare the change in quantitative ¹⁸F-FDG PET/CT parameters over time with the addition of ixazomib to lenalidomide.

3. Selection of Patients

Each of the criteria in the checklist that follows must be met in order for a patient to be considered eligible for this study. Use the checklist to confirm a patient's eligibility. For each patient, this checklist must be photocopied, completed and maintained in the patient's chart.

In calculating days of tests and measurements, the day a test or measurement is done is considered Day 0. Therefore, if a test is done on a Monday, the Monday four weeks later would be considered Day 28.

ECOG-ACRIN Patient No. _____

Patient's Initials (L, F, M) _____

Physician Signature and Date _____

NOTE: CTEP Policy does not allow for the issuance of waivers to any protocol specified criteria (http://ctep.cancer.gov/protocolDevelopment/policies_deviations.htm). Therefore, all eligibility criteria listed in Section 3 must be met, without exception. The registration of individuals who do not meet all criteria listed in Section 3 can result in the participant being censored from the analysis of the study, and the citation of a major protocol violation during an audit. All questions regarding clarification of eligibility criteria must be directed to the Group's Executive Officer ([contact]) or the Group's Regulatory Officer ([contact]).

NOTE: Institutions may use the eligibility checklist as source documentation if it has been reviewed, signed, and dated prior to registration/randomization by the treating physician.

NOTE: This study involves pre-registration and randomization. Bone marrow specimen must be submitted for central MRD assessment and results will determine Step 1 eligibility. Patients will not be randomized without MRD results.

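### The OS hazard ratios by baseline PET status are provided for only when the interaction test is significant, so the within-subgroup comparison in objective 2.5.2 is reported selectively and often not at all

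*Combined protocol and SAP*

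**What the plan says.** Section 2.5 (objective 2.5.2) sets the aim: "To compare overall survival (OS) with the addition of ixazomib to lenalidomide among baseline" PET-positive and PET-negative subgroups. Section 12.1.3.2, aim [2], puts it into operation: "This secondary imaging aim consists of a subgroup analysis of the trial primary endpoint, and will assess for heterogeneity of treatment effect" by baseline PET status. The method is stated as "Heterogeneity of treatment effect will be assessed at full information, using a two-sided statistical test for interaction between study arm" and PET status in a Cox model.

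Two branches follow:
- Not significant: "If the statistical test for interaction is not significant at the 0.05 level, we will conclude that there is not sufficient evidence for heterogeneity". No subgroup hazard ratio, CI or interaction estimate is listed.
- Significant: "if the statistical test for interaction is significant, estimated treatment hazard ratios for OS (ixazomib arm vs. placebo arm) will be reported separately" for the two PET subgroups, with 95% CIs.

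No other section supplies treatment hazard ratios for OS by PET status. Section 12.1.3.1 also fits an arm-by-PET interaction, but there the quantity estimated is the prognostic effect of PET, not the effect of ixazomib. Power is stated for aims [1] and [3] and not for aim [2].

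**The concern.** The objective asks for an effect of treatment in each PET subgroup. The plan makes the display of that effect depend on a p-value, which has two consequences.

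First, in the non-significant branch the reader has a verdict with no estimate or interval beside it, and cannot tell evidence of similar effects from lack of information.

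Second, the estimates that do appear have been selected for being far apart. Section 12.1.3.2 says that detected heterogeneity would point to a possible gain from choosing patients by PET status. Such an inference would start from a contrast that is, on average, too large. With no power stated for this aim, the plan does not show how weak the test is.

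**Working it through.** **Inputs.** 179 deaths at full information, 510 patients, 3.5 years of accrual, analysis at 6 years, control median OS 5.5 years, HR 0.65, one-sided 2.5% (section 9.4). 1:1 allocation (section 9.6). Up to 10% without a usable baseline scan: "the proposed sample size of 510 patients (459 evaluable") (section 12.1.3.1). PET prevalence: "We anticipate between 50-70% of patients will have a positive" scan (section 12.1.3.2).

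**The plan's own figures first.** With exponential survival and hazard λ = ln 2/5.5 = 0.126 per year, expected deaths per arm are 255 × [1 − (e^(−2.5λ) − e^(−6λ))/(3.5λ)]. This gives 104.5 (control) + 74.4 (hazard 0.65λ) = 178.9, against 179 stated. Power is Φ(√179/2 × |ln 0.65| − 1.96) = Φ(2.88 − 1.96) = 82%, or 79% with the final group-sequential critical value 2.0858. Both agree with the stated approximate 80%, so the event count is a sound basis.

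**Precision of the interaction.** With 1:1 allocation, the standard error of the log ratio of the two subgroup hazard ratios is SE = √(4/d₊ + 4/d₋), where d₊ and d₋ are deaths in PET-positive and PET-negative patients.

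Base case: 179 × 0.9 = 161.1 deaths, split 60/40 into 96.7 and 64.4.
- SE = √(0.0414 + 0.0621) = 0.322.
- Smallest observed ratio that reaches significance: exp(1.96 × 0.322) = 1.88.
- Ratio detected with 80% power: exp(2.80 × 0.322) = 2.46.

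**Range.** Deaths may fall disproportionately among PET-positive patients. Section 12.1.3.1 plans on median PFS of 19 vs 26 months, a hazard ratio of 26/19 = 1.37. If that carried over to OS (an assumption), 70% prevalence would put about 75% of deaths in PET-positive patients. The chance of release is P(|Z| > 1.96) with Z centred at ln(true ratio)/SE.

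| Deaths | Share of deaths PET-positive | SE | Smallest significant ratio | Ratio for 80% power | Released if true ratio 1.5 | Released if 2.0 |
|---|---|---|---|---|---|---|
| 161 | 50% | 0.315 | 1.85 | 2.42 | 25% | 60% |
| 161 | 60% | 0.322 | 1.88 | 2.46 | 24% | 58% |
| 161 | 70% | 0.344 | 1.96 | 2.62 | 22% | 52% |
| 161 | 75% | 0.364 | 2.04 | 2.77 | 20% | 48% |
| 179 | 50% | 0.299 | 1.80 | 2.31 | 27% | 64% |
| 179 | 60% | 0.305 | 1.82 | 2.35 | 26% | 62% |
| 179 | 75% | 0.345 | 1.97 | 2.63 | 22% | 52% |

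With no heterogeneity the chance of release is 5% by construction.

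**What is released, given significance** (base case; geometric mean of the released ratio, and its log divided by the true log):

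| True ratio | Released | Mean released ratio | Inflation of log ratio |
|---|---|---|---|
| 1.25 | 11% | 2.2 | 3.5-fold |
| 1.54 | 27% | 2.29 | 1.9-fold |
| 2.0 | 58% | 2.49 | 1.3-fold |
| 2.5 | 81% | 2.78 | 1.1-fold |

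For scale, 1.54 = 1.0/0.65: the design effect in one PET subgroup and no effect in the other.

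**Cross-check.** A patient-level exponential simulation (459 patients, 60% PET-positive, 6,000 replicates) gave release in 27-30% of trials at a true ratio of about 1.54 and in 57-58% at 2.0, with mean released ratios of 2.25-2.29 and about 2.5.

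**The case against.** Testing for interaction before interpreting subgroups is a recognised safeguard. That stands, and nothing here argues against the test. The issue is that showing the estimates depends on it, when only their interpretation needs to.

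The text never says that subgroup estimates are reported only after significance. That is literally true. But the two branches are paired, one yielding estimates and the other a verdict, and no other section fills the gap. If reporting was always intended, one sentence settles it.

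Three stronger readings are tempting and are not supported:
- A reader might infer that the aim goes unanswered whenever the test fails. It does not: section 12.1.3.2 frames the aim as assessing heterogeneity, and that question gets a test result in every case. What is missing is the pair of within-subgroup effects named in objective 2.5.2. How often it is missing depends on a true ratio that the documents do not give; at a ratio of 2 release is about as likely as not, or somewhat likelier.
- A reader might infer that the plan commits to selecting patients for ixazomib from these estimates. It says only that detected heterogeneity would point to a possible gain from doing so.
- A reader might infer that the hazard ratios are wrongly estimated. They are not. In a trial with a significant interaction, the same numbers would appear under the plan and under full reporting. The overstatement is an average over trials that pass the filter, and need not hold in any one trial.

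**Conclusion.** The concern holds in a limited form. As written, the plan provides PET-subgroup OS hazard ratios and CIs in the significant branch alone, so the comparison in objective 2.5.2 is not supplied otherwise. Release would occur about 5% of the time with no heterogeneity, about 20-27% at a true ratio of 1.5 and about 48-64% at 2.0. In the base case, overstatement on the log scale, given release, averages about twofold near a ratio of 1.5 and about 10% at 2.5.

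This rests on 161-179 deaths among scanned patients, 50-75% of them in PET-positive patients, equal allocation within subgroups and a normal approximation. The true ratios are assumed. The 80%-power ratio is best given as roughly 2.3 to 2.8; a single figure such as 2.5 depends on the number of deaths among scanned patients and their split by PET status. The aim is a secondary imaging correlative and has no bearing on the primary OS test, but the gap is worth closing because it is simple to close.

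**What to change.** In section 12.1.3.2, aim [2]:
- Report the OS hazard ratio (ixazomib vs placebo) with 95% CI in PET-positive and in PET-negative patients, and the ratio of the two hazard ratios with its 95% CI, whatever the interaction p-value.
- Keep the two-sided interaction test as the guide to interpretation.
- State that 80% power is reached only for a ratio of roughly 2.3 to 2.8, depending on the number of deaths among scanned patients and their split by PET status.

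In the base case the 95% CI factors are ×/÷ 1.49 (PET-positive), ×/÷ 1.63 (PET-negative) and ×/÷ 1.88 (ratio). An HR of 0.65 in each subgroup would then be shown as 0.65/1.49 to 0.65 × 1.49, or 0.44-0.97, and 0.65/1.63 to 0.65 × 1.63, or 0.40-1.06. That makes the imprecision plain and is itself a guard against over-reading. Full reporting does not shrink a significant contrast; it ends the selection.

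The cost is wording only, with no change to sample size, data collection, alpha or the primary analysis.
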